4.4.2 OPTIONAL FLOWCHART

4.5 RANDOMIZATION AND MASKING

Subjects will be randomly assigned to either JJVCI Investigational Contact Lens (Test) or ACUVUE OASYS (Control) groups based on a computer-generated randomization schedule prepared before the study by the sponsor Biostatistician. The randomization will be stratified by study site and randomly permuted blocks of 4 assignments will be used to achieve 1:1 Test versus Control lens type ratio within each study site.

The study site must follow the randomization scheme provided and complete enrollment according to the randomization list and not pre-select or assign subjects. The randomized assignment of subjects will be performed at the first visit prior to the first fitting. The following must have occurred prior to randomization:

- Informed consent has been obtained
- Subject meets all the inclusion / exclusion criteria
- Subject history and baseline information has been collected

This is a partially subject masked study. The dynamic nature (variable shade) of the Test lens makes full masking impossible. However, the identity of the Control lenses will be masked to the subject by way of investigational foil. This will reduce the likelihood that habitual wearers of ACUVUE OASYS recognize the Control lens and increase the likelihood that questionnaires will be answered unbiasedly.

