4.7 DETAILED STUDY PROCEDURES

4.7.1 SEQUENCE OF EVENTS

Habitual Subjects must enter the study wearing their habitual hydrogel lenses for the purposes of accurately responding to the Baseline Questionnaires.

VISIT 1: SCREENING		Day 0
The following information will be recorded:		
Step	Details	
1	Statement of Informed Consent Each subject must read, understand and sign the Statement of Informed Consent before being enrolled in the study (attached separately). A witness must also sign the form. Note: The subject must be provided with a signed copy of this document.	
2	Demographics Date of birth, gender, race, ethnicity, and global ID.	

VISIT 1: SCREENING		Day 0	
The following information will be recorded:			
Step	Details		
3	Case History	Questions regarding the subject's general health and medical history, including concomitant medications. Habitual medications taken by successful soft contact lens wearers are considered acceptable. Note that habitual medications should be continued throughout the study period.	
4	Habitual Contact Lens Type	Questions regarding the subject's habitual contact lens, including: lens name, base curve, diameter, power, and lens wearing modality.	
5	Current Contact Lens Wear Times	Record the habitual wear time (WT) and comfortable wear time (CWT).	
6	Eligibility at Screening	All responses to Inclusion Criteria questions must be answered "yes," and all responses to Exclusion Criteria questions must be answered "no" for the subject to be considered eligible.	

VISIT 1: BASELINE INFORMATION		Day 0	
The following information will be recorded:			
Step	Details		
1	Spherical Over-refraction	Perform a spherical over-refraction OD and OS. The over-refraction of their habitual lenses must be within ± 0.25 D OD and OS. Subjects outside of this range will not be allowed to participate in the study.	
2	Glare Questionnaire	The subject will respond to the Eyestrain Caused by Glare Questionnaire in regards to their habitual lenses.	
3	Project-Specific Questionnaire	The subject will respond to the Project-Specific Questionnaire	
4	CLUE Baseline Questionnaire	The subject will respond to the CLUE Baseline Questionnaire	
5	GSI Background Questionnaire	The subject will respond to the GSI Background Questionnaire	
6	Activity History Questionnaire	The subject will respond to the Activity History Questionnaire	

VISIT 1: BASELINE INFORMATION		Day 0
The following information will be recorded:		
Step	Details	

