7	Visual Acuity	Record the distance Snellen visual acuity with the habitual lenses (OD, OS, and OU) to the nearest letter. Smaller lines must be shown until the subject incorrectly identifies at least 50% of the letters.
8	Remove Habitual Lens	The subject's habitual lenses will be removed and stored in their own lens case. If they forgot to bring their lens case, one will be provided to them.
9	Slit Lamp Findings	FDA Slit Lamp Classification Scale (████) will be used to grade the findings and will be used to determine eligibility. Record only whole numbers. If any of these slit lamp findings are grade 2 or higher, the subject is ineligible to continue; complete the Final Evaluation.
10	Iris Color	The investigator will record the subject's iris color based on the scale provided (Appendix B).
11	Keratometry	Record the keratometry readings OD and OS in diopters. This can come from any appropriate instrument so long as the same instrument is used at the Final Evaluation.
12	Subjective Refraction	The investigator will complete a subjective refraction (sphere and cylinder) and record the resultant distance visual acuity OD, OS, and OU to the nearest letter. Best corrected Snellen distance visual acuity (BVA) must be 20/25+3 or better in each eye.
13	Eligibility at Baseline	All responses to Inclusion Criteria questions must be answered "yes," and all responses to Exclusion Criteria questions must be answered "no" for the subject to be considered eligible.
14	Eye Rinse	The study coordinator, investigator, or technician will rinse the subject's eyes thoroughly with saline.

VISIT 1: Lens Assignment #1		Day 0
The following information will be collected:		
Steps	Details	
1	Lens Information	The Lens Randomization Table will be used to determine which study lens is worn. The lens powers are based on the vertexed (12mm), spherical equivalent subjective refraction (Appendix A). The investigator or subject will place the lenses on. Quickly check for any lens damage and replace if necessary.

VISIT 1: Lens Assignment #1			Day 0
The following information will be collected:			
Steps	Details		
2	Lens Damage	Lens damage (draw in source document and describe). Replace lens if damaged and complete the Product Quality Complaint form and save lens in vial with saline.	

VISIT 1: FITTING #1			Day 0
The following information will be collected:			
Steps	Details		
1	Time Interval	Please wait at least 5 minutes before continuing.	

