2	Spherical Over-refraction	Perform a spherical over-refraction OD and OS using any acceptable means (i.e., phoropter, trial lenses, flipper bars) in normal room illumination and record the resultant distance Snellen visual acuity OD and OS. A 0.00 D spherical over-refraction must be achieved to continue.	
3	Lens Modification Criteria	The lens power will be modified if the over-refraction is ± 0.25 D or more in either eye. One modification attempt is allowed.	

VISIT 1: TRIAL FITTING LENS MODIFICATION			(If needed, one modification is allowed)
The following information will be collected:			
Steps	Details		
1	Lens Information	The lens power will be chosen based on the over-refraction results from the first trial lenses.	
2	Lens Damage	Lens damage (draw in source document and describe). Replace lens if damaged and complete the Product Quality Complaint form and save lens in vial with saline.	
3	Time Interval	Please wait at least 5 minutes before continuing.	
4	Spherical Over-refraction	Perform a spherical over-refraction OD and OS using any acceptable means (i.e., phoropter, trial lenses, flipper bars) in normal room illumination and record the resultant distance Snellen visual acuity OD and OS. If a 0.00 D spherical over-refraction OD and OS is not demonstrated, the subject is terminated from the study; complete the Final Evaluation.	

VISIT 1: FITTING #1, CONTINUED

Day 0

The following information will be collected:

Steps		Details	
1	Subject-reported Ocular Symptoms	The subject will respond to a Symptoms Questionnaire.	
2	Dispensing Questionnaire	Subjects will respond to the Dispensing Questionnaire for initial comfort and vision (ID: ISOC0001, ISOV0001)	
3	GSI Post-Fit Questionnaire	Subjects will respond to the GSI Post-Fit Questionnaire.	
4	LogMAR (ETDRS) Visual Acuity	
Using the Sekonic light meter with ISO1 setting of 125 under high illumination (>7.3 EV) and high chart luminance (9.9-10.7 EV) record the distance ETDRS high contrast:
 
 1. OD: Chart HC1 2. OS: Chart HC2 3. OU: Chart HC3 	

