8.5 ADVERSE EVENTS FOLLOW-UP

It is the Investigator's responsibility to maintain documentation of each reported adverse event. All adverse events will be followed in accordance with applicable licensing requirements. Such documentation will include the following:

- Adverse Event (Diagnosis not symptom)
- Detailed drawings or photographs, when appropriate
- Date and time of onset
- Date and time of resolution
- Adverse event intensity and classification, as applicable
- Treatment regimen instituted, including concomitant medications prescribed, in accordance with applicable licensing requirements
- Any referral to another health care provider if needed
- Outcome, ocular damage (if any)
- Likely etiology.
- Best corrected visual acuity at the discovery of the event and upon conclusion of the event

In addition, if an infiltrate(s) is present, the Investigator will complete the Corneal Infiltrate Assessment Form / eCRF.

Photographs or video recordings may be collected at the Investigator's discretion for purposes of documenting adverse event findings.

Visual acuity (best corrected) should be recorded prior to the report of an adverse event (as part of the Baseline Evaluation), upon the subject's report of the adverse event, and after the adverse event has resolved.

Subjects who present with an adverse events should be followed by the Investigator, within licensure, until all signs and symptoms have returned to pre-treatment status, stabilized, or been satisfactorily resolved. If further treatment (i.e. beyond licensure) is required, the patient will be referred to the appropriate health care provider. The Investigator should use his/her clinical judgment as to whether or not a subject (eye) reporting with an adverse event should continue in the study. If a subject is discontinued from the study, it will be the responsibility of the Investigator to record the reason for discontinuation. The investigator will also complete the Adverse Event Classification (AEC) Outcome form / eCRF. Any subjects with ongoing adverse events related to the test article as of the final study visit date should be followed to resolution of the adverse event or until referral to an appropriate health care provider, as recommended by the Investigator.

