6.2. Safety Endpoint(s)

6.2.1. Definition

The primary safety endpoint is the frequency per eye of any corneal infiltrate or any grade 3 or higher SLF including conjunctival injection, corneal edema, corneal neovascularization, corneal staining, tarsal abnormalities, or any other complications. SLFs will be evaluated using the FDA grading scale ranging from 0 to 4, with grade 0 represents the absence of findings and 1 to 4 representing successively worse findings (i.e. Grade 1 = trace, Grade 2 = Mild, Grade 3 = moderate and Grade 4 = severe).

The safety endpoint will be evaluated at 1-, 2-, 4-, 8- and 12-week follow-up visits and during unscheduled visits. Events occurring during an unscheduled visit will be counted in the subsequent scheduled visit. For example, if a SLF grade 3 or higher occurs between Visit 1 and Visit 2, it will be counted in Visit 2. If there are multiple events at a given time point for one eye, it will be counted only once.

The secondary safety endpoint is the frequency per eye of any reported ocular symptoms, problems, or complaints.

The safety endpoints will be evaluated at 1-, 2-, 4-, 8- and 12-week follow-up visits and during unscheduled visits. Events occurring during an unscheduled visit will be counted in the subsequent visit. For example, if an ocular symptom, problem, or complaint is reported between Visit 1 and Visit 2, it will be counted in Visit 2. If there are multiple events at a given time point for one eye, it will be counted only once.

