Reported ocular symptoms, problems or complaints (0 = No, 1 = Yes) at any visit will be analyzed using a GEE model for clustered binary outcome to assess the difference between the Test and Control groups. The regression model will include terms for lens group, time (1-, 2-, 4-, 8- and 12-week) and the lens group by time interaction. Appropriate working correlation matrix will be selected to take on consideration the correlation between measurements within each subject using Quasi-likelihood Information Criterion (QIC). Working correlation structures to be considered will include exchangeable, autoregressive AR(1) and unstructured (UN).

If the interaction lens by time is significant at the 15% significance level, the difference between the Test and Control will be assessed for each follow-up visit.

For unadjusted estimates the odds ratio of outcome 1 between the Test and the Control groups will be calculated with a 95% confidence interval to test for the difference between the Test and Control groups. For adjusted estimates the odds ratio of outcome 1 between the Test and the Control groups will be calculated with a simultaneous 99% confidence interval to test for the difference between the Test and Control groups.

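### The Symptoms Questionnaire is first given with the assigned lens already on the eye, so the secondary safety endpoint has no pre-randomization value to check, adjust for or report against

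*Protocol*

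**What the plan says.** Protocol 4.5 fixes the order at Visit 1: "The randomized assignment of subjects will be performed at the first visit prior to the first fitting". In 4.7.1 the Baseline Information block, completed before assignment, contains five questionnaires: Glare, Project-Specific, CLUE Baseline, GSI Background and Activity History (the last being "The subject will respond to the Activity History Questionnaire"). Habitual-lens acuity, lens removal, slit lamp, iris color, keratometry and refraction follow. Then comes Lens Assignment #1: "The Lens Randomization Table will be used to determine which study lens is worn". The lenses go on, there is a wait of at least 5 minutes, and an over-refraction is done. Only then, as step 1 of Fitting #1 Continued, does the first symptoms step appear: "The subject will respond to a Symptoms Questionnaire". Both schedules of events (1.8 and 4.4.1) agree: Symptoms is unticked under Baseline and ticked under Trial Fit & Dispense, Follow-up and Unscheduled.

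SAP 6.2.1 defines the endpoint: "The secondary safety endpoint is the frequency per eye of any reported ocular symptoms, problems, or complaints". It is evaluated at 1, 2, 4, 8 and 12 weeks and at unscheduled visits. SAP 6.2.2 gives the analysis: "Reported ocular symptoms, problems or complaints (0 = No, 1 = Yes) at any visit will be analyzed using a GEE model", with terms for lens group, time and their interaction. There is no baseline symptom term and no rule separating new or worsened symptoms from those already present. Protocol 9.1 lists the same terms.

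**The concern.** Every subject is an established soft lens wearer (inclusion criterion 8) and may arrive with symptoms. A symptom carried in from the habitual lens that persists or recurs counts at weeks 1 to 12 in the same way as one that starts on the study lens. Without a value taken before assignment, three things are lost. Stable differences between subjects stay in the error. A chance difference between arms in pre-existing symptoms can be neither seen nor adjusted for. The symptom percentages in each arm cannot be set against what the same people reported beforehand.

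Lost precision matters more than usual here because the hypothesis is that Test and Control are statistically no different. A noisier comparison makes that outcome easier to reach, which is the unhelpful direction for a safety endpoint.

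The contrast with eyestrain suggests an oversight. For that endpoint the plan does take a pre-randomization value: "The subject will respond to the Eyestrain Caused by Glare Questionnaire in regards to their habitual lenses". Habitual wear time and slit lamp grades are also recorded before assignment.

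**Working it through.** **1. Could anything already planned serve as the baseline?**
- The Visit 1 post-fit response is taken with the assigned lens on the eye. Protocol 4.5 also concedes that the Test lens cannot be fully masked. It is not a lens-free value, and it is not a time point in the model.
- Habitual-lens symptoms at Visits 6 to 8 come after 12 weeks of study lens wear.
- CLUE Baseline and Project-Specific items may touch on symptoms. Their text is not shown, and the plan uses neither for this endpoint.

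So this instrument gives no pre-randomization value.

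**2. Chance imbalance.** There is no stated figure to reproduce: SAP Tables 2 and 3 cover only slit lamp findings and visual acuity. Take N = 50 completers per arm (SAP 1.5) and an assumed prevalence b of pre-existing symptoms. The between-arm difference has SD = sqrt(2·b·(1−b)/50). At b = 0.30:
- SD = sqrt(2 × 0.30 × 0.70 / 50) = sqrt(0.0084) = 0.092
- 95% range = ±1.96 × 0.092 = ±0.18, or about 18 points
- Probability of a gap of 10 points or more, either way: about 28%

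At b = 0.10 the range is about ±12 points and that probability about 10%. At b = 0.50 they are about ±20 points and 32%.

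**3. Absolute rates.** If a share b has persistent symptoms and the study lens induces symptoms at rate r in the rest, the reported rate is b + (1−b)·r. With assumed r of 10% and 30%:
- b = 0: 10% and 30%
- b = 0.20: 0.20 + 0.80 × 0.10 = 28% and 0.20 + 0.80 × 0.30 = 44%

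The planned tables cannot tell these situations apart.

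**4. Power gained from one baseline yes/no.** All inputs except N, the five visits and the two-sided 5% level are assumptions. Data are random-intercept logistic. Each subject's baseline answer comes from a habitual-lens propensity that correlates at r with the study-lens propensity and carries no lens effect. The analysis is a GEE with logit link, independence working correlation, robust standard errors, and lens plus time, with and without the baseline answer.

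With identical propensity (r = 1):

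| Control prevalence | Subject SD | Conditional OR | Power without | Power with | Gain |
|---|---|---|---|---|---|
| 30% | 1.5 | 2.5 | 67% | 76% | 9 points |
| 35% | 2.0 | 3 | 64% | 77% | 13 points |
| 40% | 2.5 | 4 | 67% | 84% | 17 points |

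Each row rests on 1,500 simulated trials, so one power figure has a standard error of about sqrt(0.67 × 0.33 / 1500) = 1.2 points.

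Gain across scenarios as the correlation falls:

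| Correlation of habitual- and study-lens propensity | Gain in power |
|---|---|
| 1.0 | about 8-17 points |
| 0.7 | about 5-6 points |
| 0.5 | about 2-4 points |
| 0.3 | about 0-1 point |

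The size of the test was between 5% and 6.5% in the runs, with no consistent inflation from adding the covariate.

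**The case against.** The strongest reply is that the endpoint as defined needs no baseline. It is any reported symptom, compared between concurrently randomized arms, and nothing in the plan promises new-onset or lens-attributed symptoms. That stands, and it rules out several stronger readings.

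- **Bias.** A reader might infer that carried-in symptoms are wrongly charged to the Test lens. They fall on both arms alike in expectation, so the contrast is not systematically biased.
- **Adverse-event follow-up.** Protocol 8.5 follows subjects "until all signs and symptoms have returned to pre-treatment status, stabilized, or been satisfactorily resolved", and a reader might infer that the questionnaire leaves this unworkable. That sentence governs adverse events, which have their own baseline: case history at screening, events before lens exposure recorded as medical history, and conditions present at screening treated as baseline (4.7.1 and 8.4). It also accepts stabilization or satisfactory resolution.
- **New-onset symptoms.** A reader might infer that they can never be reported. The questionnaire and the symptoms procedure are not shown, and the form may ask about onset or attribution. What can be said is that the planned model makes no use of such a distinction.
- **A large power gain.** The upper figures require habitual-lens symptoms to predict study-lens symptoms as well as another study-lens visit would. Subjects arrive in varied lenses, including daily disposables, and all are supplied with one care solution, so a lower correlation is plausible. The simulation also departs from the plan: SAP 6.2.2 lists exchangeable, AR(1) and unstructured for symptoms, not independence. It includes a lens-by-time term that the simulation omits, and the endpoint is per eye.
- **Full recovery of the induced difference.** The rates at b = 0 in step 3 are not what a baseline covariate would restore. They show only how the reported percentages mix.

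The study is also declared exploratory, with a sample size not derived from a calculation, so no powered claim rests on this endpoint.

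**Conclusion.** The point holds as a cheap improvement. The Symptoms Questionnaire has no pre-randomization administration, and the symptom model has no term that uses one. The Test-Control comparison remains valid. It loses some precision, any chance imbalance in pre-existing symptoms stays invisible (at an assumed 30% prevalence, a gap of 10 points or more has probability about 28%), and each arm's symptom rate mixes old with new. The gain in power from a baseline covariate runs from near zero to about 17 points. It is governed mainly by how well habitual-lens symptoms predict study-lens symptoms, which the documents do not tell us. The case for the change does not need the upper end of that range, since the balance check and the interpretable rates come at almost no cost whatever the correlation.

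**What to change.** - **Protocol 4.7.1, Visit 1 Baseline Information:** give the existing Symptoms Questionnaire with the habitual lenses on, next to the Glare Questionnaire and before lens removal.
- **Protocol 1.8 and 4.4.1:** tick Baseline in the Symptoms row.
- **SAP 6.2.2:** add baseline symptom status as a covariate in the symptom GEE, at the eye level if the form records by eye. Leave the other planned terms as they are.
- **SAP tables:** show baseline symptoms by lens, and symptoms at follow-up that were not present at baseline, by lens.

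The cost is one more use of a form already given later at the same visit, a wording change in the protocol and one model term. The downside is a slightly longer Visit 1. If enrollment is already complete, state the limitation in the report and describe the endpoint as all-cause reported symptoms.
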